8.1.1 Subjects who are Randomized

- An AE related to cataract surgery will be recorded in the Surgical AE log table in the source documents and in the eCRF.
- AEs occurring prior to study drug administration will be recorded in the source documents only.
- AEs occurring from the start of study drug administration will be reported in the source documents and eCRF.
- Rescued subjects are considered to be treatment failures, and being rescued itself is not considered to be an AE.

- Adverse events occurring in rescued subjects will be reported in the source documents and eCRF.
- An IOP > 30 mmHg after Randomization will be reported as an AE in the source documents and eCRF.
- An IOP ≥ 21 mmHg AND an IOP increase > 10 mmHg from pre-dose baseline will be reported as an AE in the source documents and eCRF.
- Serious Adverse Events will be collected from the time of signature of the informed consent form and reported in the source documents and eCRF.

The term “severe” is used to describe the intensity of an AE; the event itself could be of relatively minor clinical significance (e.g., ‘severe’ headache). This is not the same as “serious”. Seriousness of AEs is based on the outcome of an AE and usually associated with events that pose a threat to a subject’s life or functioning.

A Treatment Emergent Adverse Event (TEAE) will be defined as any AE that occurs from the start of study drug administration through Visit 6 (POD22).

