9.5.2 Management

Investigator will use clinical judgment to determine the appropriate IOP-lowering medication to use and when to withdraw study drug and procedures, in consultation with the Study Medical Monitor.

It is important to note that prostaglandin-based IOP lowering medications are prohibited in this study.

- After randomization and start of study drug, if a subject has an IOP > 30 mmHg the Investigator may commence non-prostaglandin-based IOP-lowering medication while continuing the study drug, with appropriate follow-up at the next planned visit or at an unscheduled visit. The subject may require assessment at an unscheduled visit at the investigator's discretion.
 - If the IOP is < 30 mmHg at the next visit, the subject may continue on study drug.
 - If at the next visit, the IOP remains > 30 mmHg while on IOP-lowering medication, then the study drug may be discontinued and alternative IOP-lowering medication

may be started, after consultation with the Study Medical Monitor. The subject should continue in the study and complete the assessments indicated in Table 1 through Visit 6 (POD22) (Main Study) or Visit 7 (POD85) (Endothelial Cell Sub-study). The Study Medical Monitor should discuss the persistent elevation of IOP with the Sponsor Medical Monitor.

- After randomization and start of study drug, an IOP of ≥ 21 mmHg AND an increase > 10 mmHg from the Visit 2 (POD1)/pre-dose baseline (both criteria must be met) is considered clinically significant and the Investigator should consider starting non-prostaglandin-based IOP-lowering medication while continuing the study drug, with appropriate follow-up at the next planned visit or at an unscheduled visit.
 - If the IOP reduction is satisfactory at the next visit, the subject may continue on study drug.
 - If the IOP reduction of IOP is not satisfactory at the next visit, then the study drug may be discontinued and alternative IOP-lowering medication may be started, after consultation with the Study Medical Monitor. The subject should continue in the study and complete the assessments indicated in Table 1 through Visit 6 (POD22) (Main Study) or Visit 7 (POD85) (Endothelial Cell Sub-study). The Study Medical Monitor should discuss the persistent elevation of IOP with the Sponsor Medical Monitor.

Medications used for treating increased IOP will be recorded in the Concomitant Medications section of the eCRF, noting that they were used to reduce IOP.

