11. SAFETY ANALYSES

The extent of exposure and all safety endpoints will be summarized using the Safety population. For all safety endpoints, the observed data and scheduled visits will be used for summary statistics. No imputation of missing data will be employed.

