11.2 Adverse Events

Non-serious AEs occurring from the start of study drug administration until EOMS for the subjects in the Main study only or until EOSS for subjects in the Sub-study will be reported in the eCRF. Serious AEs (SAEs) occurring after signing the informed consent form until EOMS for the subjects in the Main study only or until EOSS for subjects in the Sub-study will be reported in the eCRF. All AEs will be coded using MedDRA version 23.1 - September 2020, and classified by SOC and preferred term.

All AEs occurring from the start of study drug administration through the last day of participation in the Main study (EOMS) are considered as TEAEs.

An overall TEAE summary by treatment group will be presented by the number of events and the number and percentage of subjects experiencing one or more events, including all TEAEs, treatment-related TEAEs, treatment-emergent SAEs, severe TEAEs, TEAEs leading to discontinuation, and death.

The number and percent of subjects reporting one or more TEAEs and the number of TEAEs will be tabulated by SOC, preferred term, and treatment group for all TEAEs. Results will be displayed in order of decreasing frequency based on the occurrence rate in the APP13007 group, both across SOC and within each SOC term. Summaries of all ocular TEAEs, ocular TEAEs in the study eye, ocular TEAEs in the non-study eye, all non-ocular TEAEs, TEAEs related to study drug, ocular TEAEs related to study drug in the study eye, non-ocular TEAEs related to study drug, treatment-emergent SAEs, SAEs related to study drug and TEAEs leading to study discontinuation will also be presented in the same manner. The number and percent of subjects reporting one or more TEAEs will also be summarized by maximum severity for all TEAEs, ocular TEAEs in the study eye and non-ocular TEAEs.

The relationship of TEAEs will be determined by the relationship to study drug and/or to the ocular surgical procedure. Ocular TEAEs related to both study drug and surgery or related to surgery only will be summarized separately.

In addition, the incidence of TEAEs occurring in at least 5% of subjects in any treatment group and incidence of non-serious TEAEs above the threshold of 5% of subjects in any treatment group (for data transparency reporting) will be presented.

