11.3.1 Intraocular Pressure

IOP assessments will be performed from Screening through EOMS for the study eye. IOP assessments will be performed at Screening and EOMS for the non-study eye.

For the study eye, the IOP data and change from baseline (POD1 pre-dose) at each post-surgery scheduled visit through EOMS will be summarized by treatment group using descriptive statistics, including 95% CI for the mean of change from baseline. The IOP change from Screening to each scheduled post-surgery visit through EOMS for the study eye will be summarized to evaluate any potential impact from IOP lowering medication use on the surgery day (Day 0). A box and whisker plot will be presented for the IOP change from baseline through EOMS and for the IOP change from Screening through EOMS for the study eye. The IOP change from POD15 to POD22 for non-rescued subjects who complete the study will be summarized for the study eye.

The IOP increase from baseline and increase from Screening will be categorized as ≤ 0 , 1-5, 6-10, >10 (mmHg). The number and percentage of subjects in each category will be tabulated at each post-surgery visit for the study eye. In addition, subjects with an IOP ≥ 21 mmHg and an increase > 10 mmHg from baseline, and subjects with an IOP > 30 mmHg at any time following initiation of study drug will be summarized and listed for the study eye.

The IOP data collected after taking rescue medication will be excluded from the summary tables and plots for the study eye.

The IOP data at Screening and EOMS, and change from Screening to EOMS for the non-study eye will be summarized using descriptive statistics.

All IOP data, including data collected after taking rescue medication, will be presented in a data listing.

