11.3.2 Best Corrected Visual Acuity

Since the BCVA endpoint will also be assessed for efficacy, this endpoint has been described in the [Section 10.2.1](#). The assessments for the study eye will be performed from Screening through EOMS for safety evaluation. The assessment for the non-study eye will be performed at Screening and EOMS.

The BCVA LogMAR scores and change from baseline (POD1 pre-dose) will be summarized descriptively by treatment group at each post-surgery scheduled visit through EOMS for the study eye. The BCVA base LogMAR scores change from baseline will be classified as ≤ 0 , $0 < - < 0.2$ and ≥ 0.2 , which are equivalent to ≤ 0 line (visual acuity improved), $0 < - < 2$ lines, and ≥ 2 lines (visual acuity worsened). The number and percentage of subjects in each category will be tabulated at each post-surgery scheduled visit for the study eye.

The BCVA LogMAR scores collected after taking rescue medication will be excluded from the summary tables for the study eye.

The BCVA LogMAR scores at Screening and EOMS, and change from Screening to EOMS for the non-study eye will be summarized using descriptive statistics.

All BCVA data, including data collected after taking rescue medication, will be presented in a listing.

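### The safety category tables for visual acuity and IOP rise leave out unscheduled visits and have no worst-value row, and the SAP does not say whether its any-time IOP summary overrides the scheduled-visit rule

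*SAP*

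**What the plan says.** The general rule in SAP Section 11 is "For all safety endpoints, the observed data and scheduled visits will be used for summary statistics".

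For visual acuity, SAP 11.3.2 classes the change from the POD1 baseline into three groups, the worst being a loss of 2 lines or more, and repeats the restriction: "The number and percentage of subjects in each category will be tabulated at each post-surgery scheduled visit for the study eye". For IOP, SAP 11.3.1 classes the increase as 0 or less, 1-5, 6-10 or more than 10 mmHg. It tabulates these by post-surgery visit without using the word scheduled, so the restriction on that table comes from Section 11. Neither table has a row for the worst value over all visits.

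SAP 11.3.1 then treats the two IOP thresholds differently. After naming an IOP of at least 21 mmHg with a rise above 10 mmHg, the same sentence continues: "subjects with an IOP > 30 mmHg at any time following initiation of study drug will be summarized and listed for the study eye". A later sentence removes IOP readings taken after rescue medication from the study-eye tables and plots. SAP 11.3.2 does the same for BCVA.

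On the AE side, Protocol 8.1.1 states "An IOP > 30 mmHg after Randomization will be reported as an AE in the source documents and eCRF", and also "An IOP ≥ 21 mmHg AND an IOP increase > 10 mmHg from pre-dose baseline will be reported as an AE".

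**The concern.** Restricting by-visit means to scheduled visits is ordinary practice. It is less suitable for a table meant to show how many eyes did badly, because an eye that does badly is more likely to be examined off schedule. Protocol 6.2.11 lists follow-up of subjects on IOP-lowering medication, and ophthalmic assessments the investigator thinks appropriate, among the reasons for unscheduled visits. Protocol 9.5.2 allows follow-up of a raised IOP "with appropriate follow-up at the next planned visit or at an unscheduled visit". After POD8 the scheduled visits are nominally 7 days apart (15 − 8 = 7; 22 − 15 = 7), which leaves room for a worst value to fall between them.

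Both measures matter to this trial. IOP increase is the first class-related ocular risk in Protocol 1.5.1.4, and a 2-line loss is the measure in the study-level halting rule in Protocol 9.1.2. What is at stake is whether the by-arm safety tables show the worst that was seen. There is a second, smaller problem: Section 11 and the any-time wording in 11.3.1 point in different directions, and a programmer would have to choose between them.

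**Working it through.** The plan states no figure to reproduce, so the check is to follow a finding made **only** at an unscheduled visit and see which outputs it reaches. The sources are SAP 11, 11.2, 11.3.1 and 11.3.2, and Protocol 7.3.1.1 and 8.1.1.

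| Finding at an unscheduled visit only | By-visit safety tables | Any-time threshold summary | TEAE tables | Listing |
|---|---|---|---|---|
| IOP > 30 mmHg, or ≥ 21 mmHg with a rise > 10 mmHg | No | Yes, on the natural reading | Yes, both are AEs by definition | Yes |
| IOP rise meeting neither threshold | No | No | Only if judged an AE | Yes |
| BCVA loss of 2 lines or more | No | None exists | Only if judged clinically relevant | Yes |

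Row 1. The TEAE route does not depend on visit type: "All AEs occurring from the start of study drug administration through the last day of participation in the Main study (EOMS) are considered as TEAEs", and the "number and percent of subjects reporting one or more TEAEs and the number of TEAEs will be tabulated by SOC", preferred term and arm. An event over threshold therefore reaches a by-arm table whatever kind of visit found it.

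Row 2. This row includes some rises in the top category. If the rise exceeds 10 mmHg but the reading stays below 21 mmHg, the POD1 value was below 21 − 10 = 11 mmHg. Such an eye belongs in the above-10 class yet meets neither threshold. Rises of 6-10 mmHg that end at 30 mmHg or less are also in this row.

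Row 3. Protocol 7.3.1.1 makes a deterioration an AE when it is clinically relevant, without a BCVA cut-off. A 2-line loss has no automatic route into any by-arm safety table.

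Direction and size. For an ever/never count, adding measurements can only move a subject into a worse class or leave the subject where they are. Leaving measurements out therefore lowers the count or leaves it unchanged. With about 185 subjects planned per arm, and a Safety population close to that, one missed subject is 1/185 = 0.54 percentage points of an arm. The documents do not say how many subjects would have their worst value off schedule, so no total can be given.

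Consistency within the SAP. Section 6.3.1 lets an unscheduled value serve as baseline. Section 6.3.5 brings unscheduled assessments between POD1 and POD15 into the efficacy windows and takes the latest value. The exclusion applies to post-baseline safety summaries only.

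**The case against.** The strongest reply is that the SAP already separates the two uses for IOP. Section 11 is general and the any-time sentence in 11.3.1 is specific. Both threshold criteria share that sentence and its closing time phrase, and a specific rule normally governs. Both thresholds are also AEs, and TEAE tables are built on a time interval. This stands, and it disposes of the reading that all safety summaries are confined to scheduled visits and that IOP spikes vanish from the tables. What remains for the thresholds is that the precedence is not written down, and that the post-rescue exclusion in the same section could be read as limiting the any-time summary.

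A reader might also infer that the protocol sends these eyes to unscheduled visits. Protocol 9.5.2 offers such a visit as one option after a raised IOP has already been found, so the qualifying reading already exists. Nothing in the protocol directs eyes with vision loss to an unscheduled visit; that is left to the investigator.

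On BCVA, three fair points can be made. A clinically relevant loss is an AE. All BCVA data are listed. BCVA is also an efficacy endpoint, so unscheduled values before POD15 can enter that analysis. None of these gives a by-arm count of 2-line losses: the first rests on judgment, the second is not a comparison, and the third is a mean change. Early-termination values are not in dispute, because SAP 6.3.4 includes that visit in the end-of-main-study definition.

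**Conclusion.** The point holds in a limited form. The BCVA change-category table and the IOP-increase category table omit unscheduled values and have no worst-value summary, so subjects whose worst value was seen only off schedule are undercounted. The BCVA gap is the more important one, because no numeric AE rule stands behind it. The IOP threshold events are not lost; the SAP only needs to say how its two rules fit together.

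The undercount cannot be quantified from the documents. It goes one way within each arm, but its effect on the difference between arms is unknown: both arms follow the same masked schedule, and nothing shows that unscheduled visits would be more frequent in one of them. The documents therefore do not support an inference that the tables favour APP13007. The conclusion assumes that Section 11 will be programmed as written and that at least some unscheduled visits include IOP or BCVA measurements. It is a cheap improvement worth making before database lock, and it does not affect the efficacy conclusions.

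**What to change.** 1. In SAP 11, keep scheduled visits for the by-visit descriptive statistics. Add a sentence saying that the IOP threshold summary in 11.3.1, for both criteria, uses all post-dose measurements including those from unscheduled visits.
2. In 11.3.1, say whether readings after rescue medication count in that summary.
3. Add one row by arm, worst post-dose value at any visit, to the BCVA change-category table (showing losses of 2 lines or more) and to the IOP-increase category table. State the post-rescue rule for these rows too, since both sections exclude such data from their tables.

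The cost is a few sentences, one row in each of two tables and a little programming. The data are already collected, because Protocol 6.2.11 requires unscheduled visits to be documented in their own eCRF pages. The any-visit counts may look slightly less favourable than the by-visit ones.

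One related item should be reconciled at the same time. Protocol Table 2 gives the AE reporting level as an IOP of 30 mmHg or more, while Protocol 8.1.1 gives it as above 30 mmHg. The two passages should agree, because the TEAE tables are the backstop for the IOP summary.

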11.1 Extent of Exposure

Exposure to study drug will be summarized by duration (days) on study drug (the number of days between the first dose date and last dose date of study drug) and total number of doses that are instilled correctly in the study eye using descriptive statistics for all subjects in the Safety population and subjects in the Sub-Study. In addition, the duration on study drug will be categorized as 1–4 days, 5–8 days, and 9–13 days, and ≥ 14 days, and the number and percentage of subjects in each category will be presented for all subjects in the Safety population and subjects in the Sub-Study. The number of doses received per subject will also be categorized as < 8 doses, 8–< 16 doses, 16–< 28 doses, = 28 doses, and >28 doses, and the number and percentage of subjects in each category will be presented by treatment group for all subjects in the Safety population and subjects in the Sub-Study.

If the date of last dose is missing, the date of the last scheduled or unscheduled visit will be used as the date of last dose to calculate the treatment duration.

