Randomization				X						
Dispense Study Drug				X						
Study Drug Dosing BID for 14 days (POD1 to POD14) ¹¹				X	X	X	X			
Dispense Diary Card (with instructions for completion)				X	X	X				
Contact Subject ¹²						X			X	
Collect Study Drug							X			
Collect and Check Diary Cards for Accuracy and Compliance					X	X		X		
AEs ⁷ and Concomitant Medications ¹³	X	X ¹⁴	X	X	X	X ¹⁵	X	X		X ¹⁵

¹ Ophthalmic assessments will be performed in the study eye only at Visits 2-5 and Visit 7 and performed on both eyes at Visit 1 (Screening) and at Visit 6 (POD22) or at subject Early Termination/Withdrawal. In the Endothelial Cell Sub-study, corneal endothelial cell parameters are measured in both eyes at Screening and in the study eye only at Visit 6 (POD22) and Visit 7 (POD85).

² Surgery must occur between one to 28 days after Screening, preferably in the morning. If, due to unexpected events, surgery is postponed and would occur > 28 days past the Screening visit, contact the Study Medical Monitor to determine which, if any, of the screening procedures should be repeated. Subjects will be determined to be a suitable candidate for surgery during a pre-surgery medical assessment, where the routine medication list prescribed by the cataract surgeon should be reviewed to rule out prohibited medications (Section 5.4.2).

³ Visit 2 (POD1) should be scheduled between 18 to 34 hours following conclusion of surgery on Day 0. All assessments done on POD1 are done prior to Randomization to ensure eligibility. Note: Women-of-childbearing-potential are eligible for enrollment if they have a negative urine pregnancy test on POD1 prior to Randomization and they agree to abstinence from sexual activity or use of highly effective method of contraception from POD1 to Visit 6 (POD22).

⁴ Visit 5 (POD15) occurs on the day after the subject completes the study drug administration for 14 days. Women-of-childbearing-potential should have a urine pregnancy test.

⁵ Visit 6 (POD22) is the last visit for subjects participating in the Main Study only. Subjects who are withdrawn early should have the Visit 6 assessments and a urine pregnancy test, if applicable, performed before they are released from the study.

⁶ Visit 7 (POD85) is the last visit for subjects participating in the Endothelial Cell Sub-study. Subjects in the Endothelial Cell Sub-study who are withdrawn early after POD22 should have the Visit 7 assessments performed before release.

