3.2 STUDY VISIT OVERVIEW

This study will include up to 7 scheduled clinic visits (including the surgery day) over a range of ~ 24 to ~ 51 days for the subjects in the Main Study who are not participating in the Endothelial Cell Sub-study, while subjects in the Endothelial Cell Sub-study will have up to 8 scheduled clinic visits (including the surgery day) over a range of ~ 87 to ~ 114 days.

Note:

- (i) The schedule of visits is the same for all randomized subjects from Visit 1 to Visit 6
- (ii) The study drug will be dosed BID for 14 days for all randomized subjects.

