6.2.5 Day of Subject Contact on POD14

POD14 is the last day of dosing. Site personnel will contact the subject on POD14 (no specific window) to remind the subject not to take study drug on POD15 and onward and to bring the

bottle of study drug and diary back to the clinical site at Visit 5 (POD15). Site personnel will contact the subject using the subject's preferred reliable method of communication, e.g., telephone call, cell phone text or email. The site staff must make an effort to ensure that the subject receives and acknowledges the receipt of the message. Method of contact and whether or not the subject was reached is to be documented in the source document.

Any AEs reported to the site during the POD14 contact must be recorded in the source documents and eCRF. Further assessment of any reported AEs may require an Unscheduled Visit on POD14 if medically significant or they may be assessed, as appropriate, at Visit 5 (POD15).

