6.2.6 Visit 5 (POD15 + 1)

All assessments will be performed as shown in the Schedule of Events (Table 1).

Ocular assessments will be performed only on the operated, study eye.

Urine pregnancy test for women of child-bearing potential.

Study drug bottle and final diaries will be collected at this visit.

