9.4.2 Management

Investigators will use clinical judgment to determine when to rescue a subject using the guidance provided in [Section 9.4.1](#) and the appropriate rescue medication to use. Rescued subjects will stop study drug and will continue in the study, and will be assessed at each subsequent visit, if possible, through completion of the Visit 6 (POD22) assessments (if participating in the Main study) or Visit 7 (POD85) assessments (if participating in the Endothelial Cell Sub-study) (Table 1) or until the Investigator has deemed the subject is stable and can be released from the study.

If a subject needs to be rescued at Visit 5 (POD15), the Visit 5 (POD15) assessments (Table 1) should be completed before the subject is administered rescue medication.

Rescued subjects will be considered treatment failures, and the need for rescue medication will not be considered as an AE.

An AE occurring at the time of rescue will be recorded in the eCRF and will be followed by the Investigator to stabilization or resolution of the AE or the end of the study (whichever comes last).

If a subject is rescued, this event will be recorded in the eCRF (not as an AE). Medications used for rescue will be recorded in the ConMeds section of the eCRF, indicating that they were used for rescue.

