9. TREATMENT COMPLIANCE

Overall treatment compliance per subject for the study eye is defined as:

Treatment compliance (%) = [Total number of doses instilled correctly / (Actual treatment duration) x 2] x100,

where the actual treatment duration is calculated as the number of days between the first dose date and last dose date of study drug.

The treatment compliance will be summarized using descriptive statistics for the Safety population. In addition, the overall treatment compliance will be further categorized as < 80%, 80% – 100% and > 100%, and the number and percentage of subjects with compliance in each category will be presented.

Subject dosing diary data will be listed.

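### SAP 11.1 imputes a missing last-dose date as the last study visit with no cap, so a 14-day course can be scored as about 22 or 85 days, and rescued or IOP-stopped subjects still in follow-up are counted as treated for 14 days or more

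*SAP*

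**What the plan says.** SAP 11.1 summarises duration on study drug by descriptive statistics and in four categories (1–4, 5–8, 9–13, and 14 or more days), for the Safety population and for the Sub-study. If the last-dose date is missing, "the date of the last scheduled or unscheduled visit will be used as the date of last dose to calculate the treatment duration". Nothing limits this to visits in the treatment period, to the time before drug return, or to the time before rescue.

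The protocol fixes when dosing can occur. Section 3.2: "The study drug will be dosed BID for 14 days for all randomized subjects". Section 6.2.5: "POD14 is the last day of dosing". Section 6.2.6, on Visit 5 (POD15): "Study drug bottle and final diaries will be collected at this visit".

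Follow-up runs well past that. The footnotes to Protocol Table 1 state: "Visit 6 (POD22) is the last visit for subjects participating in the Main Study only" and "Visit 7 (POD85) is the last visit for subjects participating in the Endothelial Cell Sub-study". Stopping drug does not always end follow-up. Section 9.4.2: "Rescued subjects will stop study drug and will continue in the study". Section 9.5.2 likewise keeps subjects whose drug is stopped for persistent raised IOP in the study through Visit 6 or Visit 7.

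SAP 9 uses a duration with the same start and end points as the denominator of treatment compliance: "where the actual treatment duration is calculated as the number of days between the first dose date and last dose date of study drug". SAP 5.2 requires at least 80% compliance for the per-protocol (PP) population.

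**The concern.** The imputed date is one on which the subject should not have been dosing and, after Visit 5, should no longer have held the bottle. The rule therefore produces durations that the regimen cannot produce.

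There are two distinct errors. For completers, the mean, median and maximum are inflated, although the category of 14 days or more is still correct. For subjects who stopped early but stayed in follow-up, the category itself is wrong: a 3-day exposure moves from the lowest group to the highest.

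At stake is an exposure table that misdescribes how long subjects received a topical corticosteroid. There is also an unanswered question: does the same imputed date enter SAP 9 compliance, and the rules keyed to last dose or treatment duration in SAP 6.3.5, 6.4.3.1 and 10.2.2.3?

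**Working it through.** **Inputs.** First dose on POD1 = Study Day 1 (SAP 6.3.4). Last planned dose on POD14. Visit 6 at POD22 ± 2 and Visit 7 at POD85 ± 4 (Protocol Table 1). About 185 randomized per arm, about 88 of them in the Sub-study (Protocol 10.4).

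**The plan's own figure.** 14 days × 2 doses = 28 doses, which matches the full-course category in SAP 11.1. Days must be counted inclusively: a plain date difference from POD1 to POD14 is 13, which would put a full course in the 9–13 category. Inclusive counting is used below.

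**Duration when the last-dose date is missing.**

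| Subject | True days (category) | Imputed days | Imputed category |
|---|---|---|---|
| Full course, Main-only | 14 (≥ 14) | 22 (window 20–24) | ≥ 14 |
| Full course, Sub-study | 14 (≥ 14) | 85 (window 81–89) | ≥ 14 |
| Rescued or IOP-stopped after day 3, followed to last visit | 3 (1–4) | 22 or 85 | ≥ 14 |
| Stopped on day 3 and withdrawn | 3 (1–4) | 4–5 | 1–4 or 5–8 |
| Stopped on day 7 and withdrawn | 7 (5–8) | 8–9 | 5–8 or 9–13 |

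The last two rows assume an Early Termination visit 1 to 2 days after stopping. Protocol 6.2.10 asks for it at termination or as soon as possible afterwards.

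**Effect on the mean.** Suppose all subjects truly complete 14 days and a proportion k have a missing date. The documents give no rate, so k is assumed to lie between 1% and 10%.

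- Main-only: 14 + (22 − 14)k = 14 + 8k, giving 14.08 at 1% and 14.8 at 10%.
- Sub-study: 14 + (85 − 14)k = 14 + 71k, giving 14.71 at 1% and 21.1 at 10%.
- Whole arm, with 185 − 88 = 97 Main-only subjects: 14 + k(97 × 8 + 88 × 71)/185 = 14 + 37.97k, giving 14.4 at 1% and 17.8 at 10%.

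One such subject in a Sub-study arm adds 71/88 = 0.81 day to that arm's mean and sets the maximum at about 85.

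**Compliance, only if the imputed date is carried into SAP 9.** Reading the formula as doses ÷ (2 × days), a subject with all 28 doses scores:

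- true dates: 28/(2 × 14) = 100%;
- POD22: 28/44 = 63.6% (58.3% to 70.0% across the visit window);
- POD85: 28/170 = 16.5% (15.7% to 17.3%).

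Both imputed values fall below the 80% cut-off.

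**With the date capped at Study Day 14 or start of rescue.** The completer scores 14 days and 100%. The subject dosed for 3 days and rescued at a POD4 visit scores 4 days, category 1–4.

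**The case against.** The strongest reply is that the rule will seldom be used. Protocol 5.1.2.2 and 5.1.2.3 have every dose dated in the diary and transferred to the eCRF, and Table 1 has diaries checked at Visits 3, 4 and 5. Rescue and its medication are recorded as well. This stands: the trigger may be rare. But no rate is given, and a rule written for the missing case should be right in that case.

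The consequences are also bounded. Duration is descriptive, with no test. The parallel table of doses received does not use the imputed date and would still show a short course. Both points stand.

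Three stronger readings are tempting, and the documents do not support them.

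- *All early stoppers are counted as fully treated.* Subjects who ask to stop are withdrawn (Protocol 6.3), and those stopped for harm or non-compliance may be (9.1.1.3, 9.1.1.4). Their last visit is normally the Early Termination visit, so the overstatement is small. Some rescued subjects may also be released before POD22 or POD85 (9.4.2).
- *The PP population is corrupted.* SAP 9 does not invoke the imputation in 11.1. A subject with 28 recorded doses but no last-dose date is also unlikely, since the same diary supplies both.
- *The arms are biased against each other.* Rescue may well be commoner on placebo if the drug works, but imbalance needs rescue and a missing date in the same subject. Nothing in the documents shows how often that would happen.

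**Conclusion.** The missing cap is a definite drafting error. Read as written, the rule scores a 14-day course at about 22 days (Main Study) or 85 days (Sub-study). It also puts rescued or IOP-stopped subjects who remain to the last visit in the wrong duration category.

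The size depends on an unknown rate of missing dates, and the 1% to 10% range is an assumption. The calculated means also assume that every subject truly completes 14 days and attends the last visit on its nominal day. For withdrawn subjects the error is slight.

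The effect on compliance and the PP population is an open question for the SAP to settle, not a demonstrated exclusion. The PP analysis is in any case only a sensitivity analysis (SAP 10.1.3). The primary ITT result is not shown to be affected. The correction is worth making before database lock because it costs almost nothing.

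**What to change.** In SAP 11.1, impute a missing last-dose date as the earliest of:

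- (a) the last scheduled or unscheduled visit, as now;
- (b) the recorded date on which study drug was stopped, if known;
- (c) the start date of rescue medication;
- (d) the date the bottle was returned;
- (e) Study Day 14 (POD14).

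Item (a) must stay in the list. Without it, a subject lost after POD4 with no rescue, no bottle return and no known stop date would be credited with dosing to POD14, which is worse than the present rule.

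State that duration is counted inclusively. State also whether the imputed date is used for compliance in SAP 9 and for the rules keyed to last dose or treatment duration in SAP 6.3.5, 6.4.3.1 and 10.2.2.3.

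The cost is a short SAP edit and a small change to one derivation. No new data are needed, and no clinical rule changes.
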